5.2 Use of co-intervention (if applicable)

All study patients will be treated with parenteral therapeutic anticoagulation. Patients will receive an intravenous (IV) bolus of 80 U/kg unfractionated heparin (UFH) immediately upon confirmation of the diagnosis 'high risk PE', before of immediately after randomisation, not to exceed a total of 8,000 U. During the CDT procedure, UFH is continued. Within 4 hours (or immediately upon completion of the reperfusion therapy), the patient should have been transitioned to either full-dose parenteral anticoagulation, either therapeutically dosed LMWH or UFH (based on local protocols). Upon stabilization (no longer need for organ support, transition to normal hospital ward) and after at least 24 hours, the anticoagulation therapy may be switched to oral anticoagulation.

5.3 Escape medication

As soon as a patient meets the predefined primary study outcome, further therapeutic management decisions will be left to the discretion of the treating physician, and are not part of this study protocol.

6. INVESTIGATIONAL PRODUCT

In this study, endovascular reperfusion of the pulmonary artery will be performed using thrombectomy and thromboaspiration. A detailed description of the investigational product will be given in Appendix D2.

6.1 Name and description of investigational product(s)

The 2 most used catheter thrombectomy devices are the FlowTriever (Inari Medical) and Indigo Aspiration/Lightning (Penumbra Inc.). Both systems are CE Mark approved for the treatment of (central) PE. A detailed description of the investigational product will be given in Appendix D2.

6.2 Summary of findings from non-clinical studies

N.A.

6.3 Summary of findings from clinical studies

We refer to Appendix K4 the 2023 NICE document on "Interventional procedure overview of percutaneous thrombectomy for massive pulmonary embolism".

6.4 Summary of known and potential risks and benefits

We refer to Appendix K4 the 2023 NICE document on "Interventional procedure overview of percutaneous thrombectomy for massive pulmonary embolism".

7. NON-INVESTIGATIONAL PRODUCT

Not applicable, as all other products used (such as cannulas, vascular dilators, echo machines, are all used in the clinical ICU setting, and all are CE marked and used within the intended use.

8. METHODS

8.1 Study parameters/endpoints

8.1.1 Main study endpoint

The primary outcome is the composite incidence of the binary endpoints of all-cause mortality, treatment failure, major bleeding and all-cause stroke at day 30.

Treatment failure in the first six hours after randomization is defined as life-threatening hemodynamic or respiratory deterioration. This deterioration is the clinical scenario if, following randomisation, the patient develops overt cardiorespiratory instability over at least 15 minutes necessitating CPR, escalation of respiratory support, or ECMO. After these first six hours, treatment failure will also be defined by increasing dosages of cardiorespiratory support (e.g. oxygen, catecholamines), and lack of improvement. Lack of improvement is defined by the presence of at least one of the following criteria: i) an equal or rising SCAI SHOCK stage (**Table 1**), ii) an equal or rising Fraction of Inspired Oxygen (FiO₂) level to maintain adequate oxygen saturation (i.e. \geq 92%), or iii) an equal or decreasing P/F ratio. Treatment failure will be determined every 6 hours starting at the moment of randomisation, until the patient is considered stable and transferable to the ward.

Upon establishing the outcome 'treatment failure' physicians are allowed to escalate therapy in whatever way they consider appropriate. Therapy crossover without meeting the primary outcome is not allowed. Major bleeding is defined as Bleeding Academic Research Consortium (BARC)3b and BARC3c bleeding (=intracranial haemorrhage).²¹ Ischemic stroke is defined as any stroke (National Institutes of Health Stroke Scale \geq 1).

All primary study outcomes will be adjudicated by an independent critical events committee. This committee will consist of an independent group of three individuals with pertinent expertise that reviews and adjudicates important endpoints and relevant AEs reported by study investigators. The committee will be blinded to treatment assignment and review safety event dossiers, which may include copies of subject source documents provided by study sites, for all reported cases where the primary outcome was met. Committee members may include (interventional) cardiologists, intensivists, pulmonologists, vascular medicine specialists, and (interventional) radiologists, as well as other experts with the necessary therapeutic and subject matter expertise to adjudicate the event categories outlined above.

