Intervention: The intervention consists of immediate thrombectomy (FlowTriever, Inari Medical or Indigo, Penumbra Inc.) without systemic/locally administered thrombolysis. Thrombectomy is performed via jugular or femoral venous access by an interventional cardiologist, interventional radiologist or vascular surgeon according to the instructions for use (IFU) for the particular device. The catheter is advanced over a preplaced guidewire across the right heart into the pulmonary arteries to the location of proximal thrombus. Procedural therapeutic anticoagulation with heparin is administered. After removal of the dilator, the thrombus is extracted by controlled volume aspiration through an aspiration catheter using a syringe or dedicated aspiration system, with multiple aspirations performed as needed. Procedural objectives will be clearly stated prior to the intervention and patient's clinical and hemodynamic status and residual thrombus will guide the investigators to determine when to terminate the procedure. Treatment success is defined as clear evidence of right ventricular Version 2.1: 16-12-2024

recompensation. The procedure must be discontinued in case of treatment failure, i.e. lack of improvement or hemodynamic deterioration, and major CDT complications such as cardiac arrest or severe haemoptysis. Complications will be solved directly, with a procedure/treatment best suitable according to the treating physician, to minimalize the risk of damage and promote patient recovery.

Main study parameters/endpoints: The primary outcome is the 30-day composite incidence of the binary endpoints of

- 1) all-cause mortality
- 2) treatment failure
- 3) major bleeding
- 4) and all-cause stroke

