Treatment failure in the first six hours after randomization is defined as life-threatening hemodynamic or respiratory deterioration. This deterioration is the clinical scenario if, following randomisation, the patient develops overt cardiorespiratory instability over at least 15 minutes necessitating CPR, escalation of respiratory support, or ECMO. After these first six hours, treatment failure will also be defined by increasing dosages of cardiorespiratory support (e.g. oxygen, catecholamines), and lack of improvement. Lack of improvement is defined by the presence of at least one of the following criteria: i) an equal or rising SCAI SHOCK stage (**Table 1**), ii) an equal or rising Fraction of Inspired Oxygen (FiO₂) level to maintain adequate oxygen saturation (i.e. \geq 92%), or iii) an equal or decreasing P/F ratio. Treatment failure will be determined every 6 hours starting at the moment of randomisation, until the patient is considered stable and transferable to the ward.

Secondary endpoints include the individual components of the primary outcome as well as DOOR at 7 days as the first secondary outcome; this is defined as (i) survival with no new severe functional limitation, no treatment failure and no adverse event; (ii) survival with new-onset severe functional limitation, but no adverse events and no treatment failure; (iii) survival with BARC3b bleeding; (iv) survival with BARC3c bleeding or ischemic stroke; (v) survival with treatment failure; and (vi) death. Further ranking will be performed by the number of days that a patient needs organ support. Organ support is defined as respiratory organ support with high-flow nasal cannula or (non-)invasive mechanical ventilation, or cardiovascular organ support with a vasopressor or inotropic agent. Other secondary outcomes include amount and mode of O₂ delivered (to be assessed at 48 hrs), ICU and hospital LOS, QoL, symptom burden, functional recovery and 1-year cost-effectiveness.

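### The Summary's rule for stopping CDT uses 'treatment failure' more broadly than the endpoint does before six hours, so an early failed procedure can leave no permitted rescue reperfusion

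*Protocol*

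**What the plan says.** The Summary, under Intervention, gives the operator a stop rule: "The procedure must be discontinued in case of treatment failure, i.e. lack of improvement or hemodynamic deterioration". It also covers major complications of the procedure. No time window or severity threshold is attached. It continues: "Complications will be solved directly, with a procedure/treatment best suitable according to the treating physician".

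The endpoint definition is the same in the Summary (Main study parameters/endpoints) and in section 8.1.1. "Treatment failure in the first six hours after randomization is defined as life-threatening hemodynamic or respiratory deterioration", made operational as the case where "the patient develops overt cardiorespiratory instability over at least 15 minutes necessitating CPR, escalation of respiratory support, or ECMO". The wider criteria start later: "After these first six hours, treatment failure will also be defined by increasing dosages of cardiorespiratory support", together with lack of improvement in SCAI stage, FiO2 or P/F ratio. On timing, "Treatment failure will be determined every 6 hours starting at the moment of randomisation".

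The same term controls switching. Section 8.1.1 says: "Upon establishing the outcome 'treatment failure' physicians are allowed to escalate therapy in whatever way they consider appropriate". Its next sentence forbids crossover in a patient who has not met the primary outcome, and section 5.3 leaves management to the physician only once that outcome is met.

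Section 5.1, the body text on the intervention, ends the procedure on the investigator's assessment and does not use the term. Section 4.4 states that bailout and clinical deterioration in the planning registry may match the trial's treatment-failure component.

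**The concern.** One term has two scopes. In the Summary it tells the operator when to abandon the allocated treatment. In section 8.1.1 it decides whether the patient has an event and whether another reperfusion treatment may be given. The two differ in the first six hours, when CDT normally takes place.

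The main stake is conduct at the bedside. The plan can require the allocated reperfusion to be stopped in a high-risk patient and at the same time bar a second reperfusion treatment. Section 11.2 itself stresses the danger of delay in these patients.

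The second stake is scoring. If rescue is given despite the bar and succeeds, the patient can count as event-free under intention to treat, although the allocated strategy failed. The definition also feeds treatment failure at days 7 and 30, the day-7 composite, and the DOOR ranks ("v) survival with treatment failure; and (vi) death").

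**Working it through.** **1. Texts side by side for the first six hours after randomisation**

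| Situation, with no other primary event | Stop CDT (Summary)? | Treatment failure (8.1.1)? | Rescue reperfusion permitted (8.1.1, 5.3)? |
|---|---|---|---|
| Instability of at least 15 min needing CPR, respiratory escalation or ECMO | Yes | Yes | Yes |
| Deterioration managed with vasopressors alone, or shorter than 15 min | Yes | No | No |
| Lack of improvement | Yes | No | No |

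The last two rows are the gap.

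**2. Length of the gap (illustration)**

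Inputs: at most 60 min from randomisation to needle (section 4.2); device times of 37 min (median) and 57 min (approximate mean) from two intermediate-risk cohorts (section 1). High-risk procedures may take longer.

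- 60 + 37 = 97 min, and 360 − 97 = 263 min (4.4 h) to the 6-hour check.
- 60 + 57 = 117 min, and 360 − 117 = 243 min (4.1 h).

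From the 6-hour check an equal SCAI stage, FiO2 or P/F ratio is enough for failure, so an unrescued non-improver is caught there.

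**3. How many patients**

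The section 1 percentages for the 53-patient high-risk registry correspond to these counts: composite 17.0% = 9/53, deterioration 15.1% = 8/53, bailout 3.8% = 2/53.

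- Composite events without deterioration: 9 − 8 = 1. Bailout without deterioration is therefore 0 or 1 of 53 (0 to 1.9%). It may be 0, because that one patient could have entered the composite through bleeding or death.
- Scaled to the CDT arm: 74 × 1/53 = 1.4 patients at most.
- One unscored rescue moves the CDT rate by 1/74 = 1.4 points, or the lysis rate by 1/37 = 2.7 points, against a planned difference of 27.5 points.

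**4. Effect on the primary analysis**

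The plan's figures reproduce. Rates of 0.465 and 0.19 give OR (0.465/0.535)/(0.19/0.81) = 3.71 and a difference of 27.5 points. Fisher's exact test at 35 and 70 patients has 80.5% power.

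Planned events: 0.19 × 74 = 14.1 and 0.46 × 37 = 17.0. The Wald test from logistic regression uses SE(log OR) = √(1/a + 1/b + 1/c + 1/d), where a to d are the four cell counts. ORs are lysis versus CDT.

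| CDT | Lysis | OR (95% CI) | p |
|---|---|---|---|
| 14/74 | 17/37 | 3.64 (1.53 to 8.69) | 0.0036 |
| 15/74 | 17/37 | 3.34 (1.42 to 7.90) | 0.0059 |
| 14/74 | 14/37 | 2.61 (1.08 to 6.31) | 0.033 |
| 15/74 | 14/37 | 2.39 (1.00 to 5.73) | 0.050 |

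One reclassified CDT patient leaves the conclusion unchanged at the planned rates. It matters only in a result already near the threshold.

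**5. Effect on DOOR**

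There are 74 × 37 = 2738 pairs. Re-ranking one CDT patient affects at most 37/2738 = 1.4% of them; one lysis patient, at most 74/2738 = 2.7%.

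**The case against.** **The body text is consistent.** The stop rule stands only in the Summary, beside a definition of procedural success, and can be read as procedural failure. Section 5.1 does not use the term, and both statements of the endpoint agree. This is fair, and it points to the remedy. It does not remove the bar on rescue, which is in section 8.1.1 itself.

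**The stop rule might be taken as permission for rescue.** A reader might infer that the Summary's wording plus the escalation clause allows early crossover. The text does not support this: the escalation clause refers to the outcome, and the next sentence bars crossover without the primary outcome. Early rescue outside the endpoint is a deviation.

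**The patient might seem to be left untreated.** That is too strong. Only crossover is barred. Oxygen, vasopressors and ventilation remain, complications may be treated directly, and section 8.4 allows withdrawal for urgent medical reasons. The early criterion is event-based and need not wait for a scheduled check. A major bleed or stroke also lifts the bar. A short grace period before scoring non-response may be deliberate.

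**The gap might seem to favour CDT or to cost power.** A reader might note that the stop rule exists only for CDT and infer a bias in its favour. However, the lysis infusion takes two hours and early non-response there is unscored too, so the direction is not established. Adding 4 points to the CDT rate would lower power at 35 and 70 patients from 82–83% to 67–69% (normal approximation), but only if rescued patients lay outside the assumed 0.19. That rate comes from a registry composite that already includes bailout.

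**The rest could go to the SAP.** The details of a sensitivity analysis can. Whether a physician may give rescue lysis at two hours cannot. The planned per-protocol analysis does not count rescue as failure under intention to treat.

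**Conclusion.** The inconsistency is in the current text and holds in a limited form. A patient whose CDT is stopped in the first six hours for non-improvement, or for deterioration that does not meet the early criterion, and who has no other primary event, has no permitted rescue reperfusion until a later event or check. The wait is about 4 hours if procedures run near the cited device times. If rescue is given as a deviation and works, the patient escapes scoring only by also meeting no later failure criterion and having no death, BARC 3b/3c bleeding or stroke to day 30.

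The statistical effect is small: 0 to about 1.4 CDT patients, assuming the registry's bailout frequency carries over to this trial. The conclusion at the planned rates does not change. The sample size is not in question. The reason to act is a clear rescue instruction applied alike at every site. Severity: minor.

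**What to change.** 1. Rename the Summary's stop rule, for example as procedural failure, so that it is distinct from the endpoint. State in sections 5.3 and 8.1.1 that rescue reperfusion is permitted in either arm when the allocated reperfusion has been stopped or completed and has failed before six hours.
2. Record every non-allocated reperfusion (systemic or local lysis, catheter or surgical) with its time and reason, and report it by arm.
3. Leave the primary composite unchanged. Add one intention-to-treat sensitivity analysis that counts any non-allocated reperfusion within 30 days as treatment failure in either arm. This also covers early rescues that item 1 permits but the primary definition does not score. Details can sit in the SAP.

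The cost is a wording amendment, one recorded item and one extra analysis. The downside is that rescue is a discretionary open-label decision, so this analysis is more subjective than the primary one. That is the reason to keep rescue out of the composite itself.

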4.2 Inclusion criteria

In order to be eligible to participate in this study, a subject must meet all of the following criteria:

- Adult patients with confirmed acute PE, i.e. contrast filling defect in a lobar or more proximal pulmonary artery on computed tomography pulmonary angiography (CTPA), or obstructive shock with echocardiographic confirmed dilatation of the right ventricle and a congested vena cava inferior, both with/without echocardiographic signs of clot in transit or deep vein thrombosis of the leg.
- 2. High risk for mortality, i.e.
 - a. post cardiac arrest (after temporary need for cardiopulmonary resuscitation), OR
 - b. obstructive shock (systolic blood pressure <90 mmHg and signs of end-organ hypoperfusion (e.g. elevated lactate levels >2 mmol/l) or the need for vasopressors (noradrenalin or adrenalin) to maintain an adequate blood pressure), OR
 - c. persistent hypotension (systolic blood pressure <90 mmHg or systolic blood pressure drop ≥40 mmHg for at least 15 minutes) not caused by new onset arrhythmia, hypovolemia, or sepsis, OR
 - d. abnormal RV function on transthoracic echocardiography or CTPA AND elevated cardiac troponin levels AND respiratory failure defined as hypoxemia (SaO2 <90%) refractory to O2 supplementation by nasal cannula or Venturi mask, requiring full face mask O2 supplementation (100% FiO2), high-flow nasal O2, or (non-)invasive mechanical ventilation.
- CDT available and technically feasible so as to allow for a randomization-to-needle time of 60 minutes or less.

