4.3 Exclusion criteria

A potential subject who meets any of the following criteria will be excluded from participation in this study:

- "Catastrophic PE", i.e. ongoing cardiac arrest and/or need for extracorporeal cardiopulmonary resuscitation (ECPR) and/or immediate indication for venoarterial extracorporeal membrane oxygenation (VA-ECMO) as judged by the responsible physician(s)
- 2. Glascow Coma Scale <8 following resuscitation for cardiac arrest

- 3. Alternative diagnosis than acute pulmonary embolism contributing largely to the acute hemodynamic and/or respiratory failure, e.g. sepsis, COPD GOLD 3 or 4, or known heart failure with NYHA Functional Classification of 4, as judged by the treating physician.
- 4. A known "do not admit to the ICU" or "do not resuscitate" directive
- 5. An absolute contraindication to systemic thrombolysis, i.e.
 - ✓ History of hemorrhagic stroke
 - ✓ Ischemic stroke in past 6 months
 - ✓ Central nervous system neoplasm
 - Major trauma, major surgery or major head injury in past 3 weeks (note: mild external laceration of the head after, e.g. syncope, does not count as major head injury, especially when a CT scan of the head shows no hematoma)
 - ✓ Active bleeding, life-threatening or into a critically organ/area; OR known severe bleeding diathesis with previous bleeding fulfilling these criteria
- 6. Reperfusion therapy (systemic thrombolysis, surgical thrombectomy or CDT/other catheter directed therapy), or placement of a non-retrieved inferior vena cava filter for acute pulmonary embolism in the past 3 months
- 7. Thrombus in transit through a patent foramen ovale.
- Known chronic thromboembolic pulmonary hypertension (CTEPH), or strong suspicion of CTEPH based on pre-existing clinical findings and combinations of signs of PE chronicity on echocardiography and/or CTPA.^{2,17}
- 9. Known hypersensitivity to systemic thrombolysis, heparin, or to any of the excipients
- 10. If, in the Investigator's opinion, or after consultation with the local PERT-team or EC-members, the patient is not appropriate for thrombectomy
- 11. Chronic use of full-dose oral or parenteral anticoagulation before presentation.
- 12. Pregnancy
- 13. Current participation in another study that would interfere with participation in this study
- 14. Previous enrolment in this study

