To assess statistical power, the probability of the primary outcome was assumed to be 0.19 in the thrombectomy arm (based on the most recent data available) and 0.46 in the systemic thrombolysis arm (corresponding with a treatment OR of 3.71 and a risk difference of 27.5%; number needed to treat 3.6). The minimum clinically important difference was set at 27.5% based on discussion within the project group, scientific societies and patient representatives, and on clinical relevance for the difference facets of the composite endpoints. The assumed ARR of 27.5% consists of 5% decrease in mortality, 21.5% reduction in treatment failure or major bleeding and 1% reduction in ischemic stroke (the latter both based on expert opinion).¹⁸ Given a power of 80%, a two-sided α -level of 5%, and a 1:2 (systemic thrombolysis:CDT) patient allocation, 35 patients are needed in the systemic thrombolysis and 70 patients in the CDT arm. Assuming 5% drop-out, 37 patients (systemic thrombolysis) and 74 patients (CDT; total 111 patients) will be recruited. The calculation was done using G*Power (version 3.1.9.6) and is based on proportion difference tested with an anticipated OR.

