8.3 Study procedures

The study starts as soon as the patients is identified as eligible for inclusion and randomised. All patients, i.e. both study arms, will be treated with an UFH bolus after diagnosis. Patients randomised to the usual care arm will be treated with UFH or LMWH with systemic thrombolysis. Patient randomised to the intervention will be treated with UFH or LMWH (see paragraph 5.2 for specifics) and transferred to the cath lab and subjected to the thrombectomy. All further diagnostic tests (e.g. echocardiography, repeated blood test) are used along clinically relevant but not dictated by this protocol. No biomarkers or imaging test at baseline or follow-up will be required for the study. The SCAI SHOCK stage will be assessed at baseline and every 6 hours starting from randomization until the patient is stabilized and transferable to a normal ward (**Table 1**).^{26,27} At 48 hours following randomisation, the amount of oxygen supplementation (I O_2 /min) is noted in the medical chart. Patients will be contacted by the Sponsor on day 7 (± 2 days), at 3 months (± 1 week), at 6 months (± 1 week), at 9 months (± 1 week) and at 12 months (± 2 weeks) by e-mail to complete the PROMS questionnaire(s) (**Table 2**).

Stage	Α	В	С	D	E
Condition	Hemodynamically	Hemodynamically	Hypoperfusion	Failure to	Extremis /
	stable	unstable	= Shock	stabilize with	refractory shock
				initial therapy	
Hypotension:					
- SBP	>90 mm Hg	60-90 mm Hg	60-90 mm Hg	60-90 mm Hg	<60 mm Hg
- MAP	>65 mm Hg	50-65 mm Hg	50-65 mm Hg	50-65 mm Hg	<50 mm Hg
		OR	AND	AND	OR
Hypoperfusion					
- Arterial lac-					
tate	<2 mmol/L	2-5 mmol/L OR	2-5 mmol/L O R	>5-10 mmol/L	>10 mmol/L
			200-500 U/L	OR	OR
- ALAT	<200 U/L	200-500 U/L	≥ 7.2	>500 U/L	< 7.2
- рН	≥ 7.2	≥ 7.2		≥7.2	
		AND	AND	OR	OR
Treatment	No Drugs	No Drugs	No Drugs	2 Drugs	≥3 Drugs OR
intensity	No Devices	No Devices	No Devices		Device
			OR	OR	OR
			1 Drug without	1 Drug with	Out-of- or in-
			hypotension or	persistent	hospital cardiac
			hypoperfusion	hypotension or	arrest
				hypoperfusion	

Table 1: SCAI SHOCK stage overview. SBP = systolic blood pressure; MAP = mean arterial pressure; ALAT = alanine aminotransferase, Drugs = intravenous vaso-active drugs, Devices = RV support or VA-ECMO; hypotension = SBP ≤90 mm Hg or MAP ≤65 mm Hg

	7 Days	3 Months	6 Months	9 Months	1 Year
EQ-5D-5L	Х	Х	Х	Х	Х
ICHOM-VTE -	Х	Х	Х	Х	Х

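### Table 1 puts no time limit on the stage E cardiac-arrest criterion, so read literally patients enrolled after an arrest always meet lack-of-improvement criterion i) once six hours have passed

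*Protocol*

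**What the plan says.** **Endpoint.** Treatment failure is a component of the primary composite. Section 8.1.1 says: "After these first six hours, treatment failure will also be defined by increasing dosages of cardiorespiratory support (e.g. oxygen, catecholamines), and lack of improvement". It continues: "Lack of improvement is defined by the presence of at least one of the following criteria: i) an equal or rising SCAI SHOCK stage". The other two criteria concern FiO2 and the P/F ratio. On timing: "Treatment failure will be determined every 6 hours starting at the moment of randomisation, until the patient is considered stable and transferable to the ward".

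**Staging.** Section 8.3: "The SCAI SHOCK stage will be assessed at baseline and every 6 hours starting from randomization until the patient is stabilized". Staging stops once ward transfer is also possible. In Table 1 the stage E column (headed as extremis or refractory shock) ends with a cardiac arrest in or out of hospital, joined by OR to the other stage E items. No time window, footnote or tie-break between columns is given.

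**Population.** Section 4.2, criterion 2a, admits patients "post cardiac arrest (after temporary need for cardiopulmonary resuscitation), OR" other high-risk features. Section 4.3 excludes an arrest that is still ongoing.

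**Other wordings of treatment failure.** The Summary's paragraph on the intervention, where it says when to stop the procedure, and section 1 both describe treatment failure as either lack of improvement or deterioration. There, lack of improvement is enough. In section 8.1.1 it is joined by 'and' to increasing support.

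**The concern.** A shock stage compared over time should be able to fall when the patient recovers. The arrest item describes an event, and for 2a patients that event precedes randomisation. If it keeps counting, their stage is held at its worst level by history, and an equal stage is recorded however well they do.

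Treatment failure feeds the primary composite at day 30, the composite at day 7, treatment failure as a secondary endpoint, and a DOOR rank. Section 8.1.1 also makes it the condition for escalating therapy and ties crossover to meeting the primary outcome. A scoring artefact could therefore affect both the outcome count and the treatment later received. The protocol also leaves room for sites to score current state instead, so two sites could classify the same course differently in an open-label trial.

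**Working it through.** **1. The text, step by step**

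- Section 4.3 excludes ongoing arrest, so at baseline the arrest item can be met only by a past arrest.
- Section 4.2, 2a, enrols exactly such patients. Under Table 1 as printed they are stage E at baseline.
- Patients are in hospital from randomisation until ward transfer, so an out-of-hospital arrest cannot fall within a scoring interval. For a trial patient those words can only describe history, which makes the literal reading a natural one.
- If the past arrest still counts at later stagings, the stage is E again, 'equal' is met, and one criterion suffices for lack of improvement.
- Lack of improvement comes into play only after the first six hours, and checks end when the patient is stable and transferable.

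**2. Consequence under each wording of treatment failure**

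- *Lack of improvement alone suffices* (Summary, section 1): any 2a patient still under assessment after six hours becomes a primary-outcome event in either arm.
- *Increasing support and lack of improvement* (section 8.1.1): the second condition is already met for 2a patients, so failure rests on increasing support alone. A 2a patient whose catecholamine dose rises while FiO2 falls and the P/F ratio improves is a failure. A patient without an arrest who has the same course and a falling stage is not.

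**3. The plan's own sample size (section 4.4)**

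Inputs: "the probability of the primary outcome was assumed to be 0.19 in the thrombectomy arm" and "0.46 in the systemic thrombolysis arm (corresponding with a treatment OR of 3.71 and a risk difference of 27.5"%; power 80%, two-sided 5%, allocation 1:2. The OR and risk difference imply 0.465 for the thrombolysis arm (0.19 + 0.275).

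- The pooled two-proportion formula without continuity correction gives 33 thrombolysis patients at 0.465 and 34 at 0.46. The plan states 35.
- Fisher exact power at 35 v 70 is 80.5% at 0.465 and 79.1% at 0.46.
- Drop-out of 5%: 35/0.95 = 36.8, rounded up to 37; 70/0.95 = 73.7, rounded up to 74; total 111.

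The stated size reproduces.

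**4. Conditional illustration of dilution**

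Assume that a share s of patients are 2a, that all of them are events in both arms, and that the planned rates hold for everyone else. Each arm's rate becomes s + (1 − s) × p, and the difference becomes (1 − s) × 0.27. For s = 0.10: 0.10 + 0.90 × 0.46 = 0.514 and 0.10 + 0.90 × 0.19 = 0.271. Power is by exact enumeration of the two-sided 5% pooled chi-square test at 35 v 70.

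| Assumed 2a share | Thrombolysis | CDT | Difference | Power |
|---|---|---|---|---|
| 0% | 0.460 | 0.190 | 0.270 | 82.5% |
| 10% | 0.514 | 0.271 | 0.243 | 69.5% |
| 20% | 0.568 | 0.352 | 0.216 | 56.5% |
| 30% | 0.622 | 0.433 | 0.189 | 43.7% |

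**The case against.** - **The protocol does not say that the arrest carries forward.** A reader might infer that 2a patients cannot leave stage E and fail at every check. That needs two rules the protocol does not state: that a pre-randomisation arrest still counts later, and that the highest matching column wins. Staging every six hours until stabilisation, and the heading of stage E, also fit a current-state reading. A patient with normal pressure, lactate and pH and no drugs matches the stage A column too. This stands. It makes Table 1 open to two readings for these patients, and that is the defect.
- **The reach is limited.** The criterion does not apply in the first six hours and checks stop at stability, so a 2a patient who recovers quickly may never be scored on it. This stands. It is not established that every 2a patient becomes an event.
- **The 'and' protects the endpoint.** Under section 8.1.1 as written, a recovering patient without increasing support is not a failure. This stands for that reading, but the Summary and section 1 word treatment failure differently. Those two places are not the endpoint definition, which is a reason to reconcile them rather than assume they govern.
- **The power figures do not isolate the arrest item.** If lack of improvement alone counted, an unchanged stage, FiO2 or P/F ratio would also create events among other patients, and 0.46 v 0.19 would not hold for them. This stands.
- **Blinded adjudication.** A three-member committee reviews reported cases in which the primary outcome was met. It can query a failure reported in a recovered patient. It does not see cases that a site scoring current state never reported, and it cannot supply a missing rule.

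**Conclusion.** The point holds as a defect of definition. Table 1 sets no time limit on the arrest criterion, 2a patients are eligible, and an equal stage alone meets lack of improvement. Read literally, criterion i) is always met for these patients after the first six hours, in both arms, whatever their current haemodynamics.

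The size depends on what the protocol leaves open. If lack of improvement alone is treatment failure, 2a patients still under assessment become primary-outcome events. Because the same rule applies to both arms, the main effect is dilution of the contrast. If increasing support is also required, the loss is smaller: criterion i) carries no information for 2a patients and their failure status rests on increasing support alone. Under either wording, sites that score current state will classify identical patients differently.

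The fall in power from about 82% to 70, 57 and 44% is an illustration only. It rests on assumed 2a shares of 10, 20 and 30%, on all 2a patients being events, and on planned rates kept for everyone else. It should not be read as a forecast.

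**What to change.** In section 8.1.1 and a footnote to Table 1, for endpoint scoring only:

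1. Count the arrest criterion only for an arrest after randomisation and within the interval being scored.
2. Record a pre-randomisation arrest separately as a baseline characteristic.
3. Score both the baseline stage and the later stages from current blood pressure, perfusion markers and drugs or devices. Changing only the later stages would leave baseline at E, and a fall would then be recorded automatically.
4. State whether 'equal' is judged against baseline or against the previous check.

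Separately, reconcile the Summary, section 1 and section 8.1.1 on whether lack of improvement alone is treatment failure.

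The cost is a few sentences, a footnote and a matching eCRF instruction. No new measurements are needed, and 2a patients already staged can be re-scored from their recorded values. These changes concern how the endpoint is scored and do not alter clinical care.
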